6.2.3. Reactogenicity Data

Reactogenicity data is solicited adverse events (AEs). The reactogenicity data collected from the e-Diary will be: local reactions (redness, swelling, and pain at injection site), systemic events (vomiting, diarrhea, chills, headache, fatigue, muscle pain other than muscle pain at the injection site, and joint pain), temperature and use of antipyretic medication.

The e-Diary will record reactogenicity data from day 1 to day 7 following booster vaccination. The analysis interval for reactogenicity data will be ‘any day 1-7’ which includes data from day 1 to day 7. The day of vaccination is considered as day 1.

Table 2. Analysis Interval for Reactogenicity Data

#	Analysis Interval	Analysis Population	Interval Start date (inclusive)	Interval Stop (inclusive)
1	Vaccination	Booster Stage Safety	Vaccination date	Vaccination date + 6 days (or until resolved day)

6.2.3.1. Local Reaction Endpoints

The local reactions collected from the e-Diary will be: pain at injection site, redness, and swelling.

Local Reaction Presence (Proportion of subjects reporting each local reaction)

For each local reaction, the derivation of whether or not the specific reaction occurred on each day and ‘any day 1-7’ will be made. The derivation of this variable is given in the table below.

Table 3. Derived Variables for Local Reactions

Variable	Yes (1) ^a	No (0) ^b	Missing (.)
Any day 1-7	Subject reports the reaction as ‘mild’ ‘moderate’ or ‘severe’ on any day 1-7	Subject reports the reaction as ‘none’ on all 7 days or as a combination of ‘none’ and missing on all 7 days.	Subject reports the reaction as missing on all 7 days.

a. For redness and swelling, ‘mild’, moderate’, and ‘severe’ categories were based on the caliper size reported from the e-Diary

b. For redness and swelling, ‘none’ means 0-4 caliper units reported in the e-Diary

[REDACTED]

Maximum Severity for Local Reaction

A caliper is used to measure the redness or swelling area. Caliper units are converted to centimeters according to 1 caliper unit = 0.5 centimeters. The grading of local reactions is listed below in Table 4 and Table 5.

Table 4. Grading of Redness and Swelling

Grades	Measurement
None	0 to 2.0 cm (0 to 4 caliper units)
Mild	2.5 to 5.0 cm (5 to 10 caliper units)
Moderate	5.5 to 10.0 cm (11 to 20 caliper units)
Severe	>10.0 cm (>20 caliper units)

Table 5. Grading of Pain

Grades	
Mild	Does not interfere with activity
Moderate	Interferes with activity
Severe	Prevents daily activity

The maximum severity (highest grading) of each local reaction within 7 days of vaccination will be derived as follows:

- = ●, if values are missing for all days 1-7;
- = 0, if the subject reports all reactions as ‘None’ or a combination of missing and none for all days 1-7
- = *highest grade* (maximum severity) within 7 days of vaccination, if the answer is not ‘None’ for at least 1 day;

Duration and Onset Day of Each Local Reaction

For subjects experiencing any local reaction (or those with derived reaction presence in Table 3), the onset day (first day of the local reaction reported via e-Diary relative to the vaccination) and the maximum duration (last day of reaction –first day of reaction +1) will be derived. Resolution of the event is the last day in which the event is recorded in the e-Diary or the date the event ends if it is unresolved during the subject diary-recording period, unless chronicity is established.

In summary, the following variables will be derived for local reactions:

1. Each local reaction on each day (up to day 7) after booster vaccination

2. Each local reaction on ‘any day 1-7’ after booster vaccination
3. Maximum severity of each local reaction on ‘any day 1-7’ after booster vaccination
4. Maximum duration of each local reaction after booster vaccination
5. Any local reaction on ‘any day 1-7’ after booster vaccination

6.2.3.2. Systemic Events Endpoints

The systemic events reported via e-Diary will be: vomiting, diarrhea, chills, headache, fatigue, muscle pain other than muscle pain at the injection site, and joint pain. See the table below for the severity scales of each systemic event.

Table 6. Grading of Other Systemic Events

	Grade 1 (Mild)	Grade 2 (Moderate)	Grade 3 (Severe)
Vomiting	1 to 2 times in 24 hours	> 2 times in 24 hours	Requires IV hydration
Diarrhea	2 to 3 loose stools in 24 hours	4 to 5 loose stools in 24 hours	6 or more loose stools in 24 hours
Headache	Does not interfere with activity	Some interference with activity	Prevents daily routine activity
Fatigue	Does not interfere with activity	Some interference with activity	Prevents daily routine activity
Chills	Does not interfere with activity	Some interference with activity	Prevents daily routine activity
Muscle pain (other than muscle pain at the injection site)	Does not interfere with activity	Some interference with activity	Prevents daily routine activity
Joint pain	Does not interfere with activity	Some interference with activity	Prevents daily routine activity

Abbreviation: IV=intravenous.

For each systemic event, the following variables will be available similar to local reactions:

1. Each systemic event on each day (up to day 7) after booster vaccination
2. Each systemic event on ‘any day 1-7’ after booster vaccination
3. Maximum severity of each systemic event on ‘any day 1-7’ after booster vaccination
4. Maximum duration of each systemic event after booster vaccination
5. Any systemic event (including fever) on ‘any day 1-7’ after booster vaccination

The derivation of these variables is similar to the derivation of the variables for local reactions ([Section 6.2.3.1](#)).

6.2.3.3. Temperature

Oral temperature will be collected in the e-Diary for 7 days (day 1 to day 7) after booster vaccination. The highest temperature for each day will be recorded in the e-Diary. The protocol defines fever as a temperature $\geq 38.0^{\circ}\text{C}$. Fever will be categorized as 38.0°C to $\leq 38.4^{\circ}\text{C}$, 38.5°C to $\leq 38.9^{\circ}\text{C}$, 39.0°C to $\leq 40^{\circ}\text{C}$, and $>40^{\circ}\text{C}$ for a given day per Protocol.

Similar to the derivations of systemic events and local reactions, fever will be derived for:

1. Fever on each day (up to day 7) after booster vaccination
2. Fever on ‘any day 1-7’ after booster vaccination
3. Highest Fever (maximum severity) on ‘any day 1-7’ after booster vaccination
4. Maximum duration of fever after booster vaccination

Temperatures $<35.0^{\circ}\text{C}$ and $>42.0^{\circ}\text{C}$ will be excluded from the analysis due to the likelihood of subject recording error.

6.2.3.4. Use of Antipyretic Medication

The use and type of antipyretic medication will be recorded in the e-Diary for 7 days (day 1 to day 7) after each vaccination.

The following variables will be derived:

1. Use of antipyretic medication on each day (up to day 7) after booster vaccination
2. Use of antipyretic medication on ‘any day 1-7’ after booster vaccination
3. Maximum duration of Use of antipyretic medication after booster vaccination
4. Onset day of antipyretic use relative to booster vaccination

6.2.4. Safety Data Collected through CRF

The relationship between (S)AEs and the investigational product (bivalent rLP2086 vaccine) will be characterized as related or not related as determined by investigators and as described in the protocol. The severity of AEs will be characterized as mild, moderate, and severe.

Adverse events will be categorized according to MedDRA.

6.2.4.1. Analysis Intervals

There will be up to 6 analysis intervals for safety data collected via case report form (CRF).

Table 7. Analysis Intervals for AE, SAE, Medically Attended Events (MAEs) and Newly Diagnosed Major Conditions (NDCMC)

#	Analysis Interval	Analysis Population	Interval Start date (inclusive)	Interval Stop (inclusive)	Safety Data
1	Stage 1	Stage 1 Safety	Enrollment	Visit 7 date – 1 day	NDCMC, AE
2	Vaccination Phase	Booster Stage Safety	Booster vaccination date (Visit 7)	Visit 8 date – 1 day	AE, SAE, MAE, NDCMC
3	Follow-up Phase	Booster Stage Safety	Visit 8 date	Visit 9 date (Visit 10 date for NDCMC)	SAE, MAE, NDCMC
4	Throughout the Booster Stage	Booster Stage Safety	Booster vaccination date (Visit 7)	Visit 9 date (Visit 10 date for NDCMC)	SAE, MAE, NDCMC, autoimmune and neuroinflammatory conditions, Days missed school/work
5	Throughout the Extended Booster Stage	Booster Stage Visit 11 Subset	Visit 7 date	Visit 11	NDCMC
6	Extended Follow-up Phase	Booster Stage Visit 11 Subset	Visit 8 date	Visit 11	NDCMC

AE = Adverse Events, SAE = Serious Adverse Events, MAE = Medically Attended Events, NDCMC = Newly Diagnosed Chronic Medical Conditions

6.2.4.2. Immediate Adverse Events

Any AE that occurred within the first 30 minutes after the investigational product administration will be classified as an immediate AE. Immediate AEs are a subset of AEs.

6.2.4.3. Research-Related Injuries

Research-related injuries (RRI) occurring within of 48 hours of a blood draw will be collected for all Stage 1 visits, and at Visit 10 and Visit 11 in the Booster Stage.

6.3. Other Endpoints

6.3.1. E-Diaries Completion

For any given day, an e-diary will be transmitted and considered as complete if all expected data (the 3 local reactions, the 8 systemic reactions (including fever), and the use of antipyretics) are available. If any of the items in the e-Diary is missing on a specific day, the e-Diary will not be transmitted and the e-Diary data will be missing for all items. When all the day for the day is complete within the e-diary, the data is transmitted to a centralized database.

The following e-Diary compliance variables will be derived as follows:

1. Compliance per day: the numerator is the number of subjects who completed (transmitted) the e-diary on a given day (day 1 to day 7) and the denominator is the total number of subjects who receive the vaccination.

2. At least 1 day: the numerator is the number of subjects who completed (transmitted) the e-diary on any 1 day and the dominator is the total number of subjects who received a vaccination.
3. At least 2 days: the numerator is the number of subjects who completed (transmitted) the e-diary on any 2 days and the dominator is the total number of subjects who received a vaccination.
4. At least 3 days: the numerator is the number of subjects who completed (transmitted) the e-diary on any 3 days and the dominator is the total number of subjects who received a vaccination.
5. At least 4 days: the numerator is the number of subjects who completed (transmitted) the e-diary on any 4 days and the dominator is the total number of subjects who received a vaccination.
6. At least 5 days: the numerator is the number of subjects who completed (transmitted) the e-diary on any 5 days and the dominator is the total number of subjects who received a vaccination.
7. At least 6 days: the numerator is the number of subjects who completed (transmitted) the e-diary on any 6 days and the dominator is the total number of subjects who received a vaccination.
8. All 7 days: the numerator is the number of subjects who completed (transmitted) the e-diary on all 7 days and the denominator is the total number who received a vaccination.

6.3.2. Demographic, Medical History, and Baseline Characteristics Variables

The demographic variables are gender, race, ethnicity, and age at time of first vaccination in the primary study. Age will be derived based on birthday. For example, if the first vaccination date is one day before the subject's 13th birthday, the subject is 12 years old.

Medical history will be categorized according to the Medical Dictionary of Regulatory Activities (MedDRA).

Physical exam will be recorded as normal, abnormal, and not done.

6.4. Covariates

The covariates are mainly based on the 'primary' studies' characteristics.

- Age at first vaccination (10-14 years vs 15-18 years)
- Gender (Female, Male)

7. HANDLING OF MISSING VALUES

7.1. Immunogenicity Data

The primary immunogenicity analyses for the study will be based on the observed, determinate observations, which is under the assumption of missing completely at random (MCAR (Scott and Hsu)¹). Missing data will not be imputed for analysis. As a sensitivity analysis, a mixed-effects model with repeated measurements (MMRM) will be utilized for the immunogenicity analysis, which assumes the missingness is at random (MAR).

The hSBA LLOQ are listed in Table 8.

Table 8. LLOQ for hSBA

Strain	LLOQ
CCI [REDACTED]	1:16
CCI [REDACTED]	1:8
CCI [REDACTED]	1:8
CCI [REDACTED]	1:8

For the calculation of GMT, values below the LLOQ will be set to 0.5*LLOQ for the primary analysis.

8. STATISTICAL METHODOLOGY AND STATISTICAL ANALYSES

8.1. Statistical Methods

Unless otherwise explicitly stated, descriptive statistics for continuous variables are: n, mean, median, standard deviation, minimum and maximum. Descriptive statistics for categorical variables are: n, percentage, and total (N).

8.1.1. Analyses for Continuous Data

For each of the 4 primary test strains, hSBA titers measured at each blood sampling time point will be logarithmically transformed for analysis and geometric mean hSBA titers will be computed at each blood sampling time point along with 2-sided 95% confidence intervals (CIs). The CIs will be constructed by back transformation of the confidence limits computed for the mean of the logarithmically transformed assay data based on Student's t distribution.

The hSBA GMT will be summarized for the primary immunogenicity populations within each primary study as well as by the subgroups as presented in [Section 6.4](#). A mixed model with repeated measurements adjusted with covariates (age at first vaccination, gender, dose group, visit, and dose group by visit interaction) will also be used to estimate the GMTs at different time points.

The empirical reverse cumulative distribution curves (RCDCs) of hSBA titer will be presented graphically for each of the 4 primary strains, and at each sampling time point.

8.1.2. Analyses for Binary Endpoints

All of the binary immunogenicity endpoints will be descriptively summarized along with exact 2-sided 95% confidence intervals (or Clopper-Pearson confidence limits) for the proportion.

The exact confidence interval for proportion will be computed using the F distribution. If r equals the number of responses and n equals the number of subjects, then it follows that $p = r/n$ is the estimate of the proportion of responses. An exact 95% confidence interval can be computed by solving the following 2 equations. For the lower limit p_L ,

$$\text{use: } p_L = \frac{rF_L}{(rF_L + (n - r + 1))} \text{ and for the upper limit } p_U, \text{ use } p_U = \frac{(r + 1)F_U}{(n - r) + (r + 1)F_U}$$

where F_L is the quantile from the F distribution for $\alpha=0.025$, with numerator degrees of freedom equal to $2r$ and denominator degrees of freedom equal to $2(n-r+1)$. F_U is the quantile from the F distribution for $\alpha=0.975$, with numerator degrees of freedom equal to $2(r+1)$ and denominator degrees of freedom equal to $2(n-r)$. When r equals 0, F_L should be set equal to 1.0 so p_L equals 0. When r equals n , F_U should be set equal to 1.0 so p_U equals 1. The confidence interval using the F distribution is described in Collett² (1991).

8.2. Statistical Analyses

8.2.1. Analysis of Primary Endpoints

The immunogenicity data will be analyzed within each primary study. The primary analysis will include the summary tables on the primary immunogenicity endpoint (proportion of subjects with hSBA titer \geq LLOQ) at each blood sampling timepoint in the primary analysis populations (mITT for Stage 1, evaluable population for Booster Stage at Visits 8 and 10) for each of the 4 primary test strains.

The analysis for immunogenicity endpoints including Visit 11 will use the subset of evaluable population for Booster stage subjects who proceed to Visit 11.

CCI [REDACTED]

CCI [REDACTED]

[REDACTED]

[REDACTED]

CCI

8.2.3. Sensitivity Analyses

A mixed-effects model with repeated measurement will be utilized to assess the effect of covariates in which both baseline and post-booster titers are modeled as dependent variables for each primary test strain. This model is using maximum likelihood estimation, therefore, it also serves as a sensitivity analyses on missing data for the GMT. To account for the intrasubject correlation among the repeated measures, an unstructured covariance matrix will be used. In case the model does not converge, further covariance structures will be explored (eg. First-order autoregressive, compound symmetry). The model will take the form

$\text{Log (hSBA)} = \text{Initial Study Group} + \text{gender} + \text{age at first vaccination} + \text{visit} + \text{Group} * \text{visit}$.
The intercept will be set as random effect.

In addition to Type III analysis output, least squares GMTs at each visit will be summarized for each strain.

These analyses will only be applied to mITT population, using ½ LLOQ to impute the hSBA values below LLOQ, for the primary strains only.

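### The sensitivity GMT model combines an unstructured covariance with a random intercept, so one covariance parameter cannot be identified and non-convergence is an avoidable risk

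*SAP*

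**What the plan says.** SAP 8.2.3 (Sensitivity Analyses) sets out one mixed model per primary strain, in which "both baseline and post-booster titers are modeled as dependent variables". The fixed effects are study group, gender, age at first vaccination, visit and group by visit. Estimation is by maximum likelihood in the mITT population. On covariance it says: "To account for the intrasubject correlation among the repeated measures, an unstructured covariance matrix will be used". If the model does not converge, "further covariance structures will be explored (eg. First-order autoregressive, compound symmetry"). After the model equation comes the sentence "The intercept will be set as random effect". The promised output is Type III tests and least squares GMTs at each visit.

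SAP 7.1 gives this model its missing-data role: "a mixed-effects model with repeated measurements (MMRM) will be utilized for the immunogenicity analysis", under missing at random. It also says that for GMTs "values below the LLOQ will be set to 0.5*LLOQ for the primary analysis", and 8.2.3 applies the same half-LLOQ rule to the mixed model. SAP 8.1.1 describes a mixed model "adjusted with covariates (age at first vaccination, gender, dose group, visit, and dose group by visit interaction"), without stating a covariance structure or any random effect.

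**The concern.** In a repeated-measures model, within-subject correlation can be carried by the residual covariance matrix, by random effects, or by a combination in which each part has something of its own to estimate. Here the residual matrix is left completely free, so a random intercept has nothing left to explain. The likelihood is flat in one direction, and the covariance parameters as written have no unique maximum.

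What is at stake is which model gets reported. The plan leaves the unstructured matrix only if the fit does not converge. A flat direction can cause that failure for reasons unrelated to the data. The analyst would then move to a more restrictive structure that the data did not call for, with no fixed order and no instruction to drop the redundant term. This model is also the check on the missing-data assumption for the GMTs, so its covariance should be settled in advance.

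**Working it through.** The documents give no figure on this point to reproduce. The check is on identifiability, followed by an illustration of what a fallback might cost.

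**Inputs.** Covariance structure, random intercept and fallbacks: SAP 8.2.3. The SAP does not name the grouping unit for the intercept; subject is the natural reading. It does not state the number of time points T either. Protocol 7.1 gives nine blood draws in this study (Visits 1 to 6, 8, 10 and 11), and Protocol 9.2 adds time points from the primary studies. Baseline and post-booster draws alone could mean four (Visits 6, 8, 10 and 11). I therefore used T from 2 to 10.

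**1. Redundancy.** With intercept variance s²_b, all-ones matrix J and unstructured residual matrix R, the marginal covariance is

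V = s²_b·J + R.

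For any c that keeps s²_b + c non-negative and R − c·J positive definite, the pair (s²_b + c, R − c·J) gives the same V. R has T(T+1)/2 free elements, which is all that V can have. The model has T(T+1)/2 + 1 covariance parameters.

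| T | Parameters, unstructured + intercept | Rank | Unstructured alone |
|---|---|---|---|
| 4 | 10 + 1 = 11 | 10 | 10 / 10 |
| 5 | 15 + 1 = 16 | 15 | 15 / 15 |
| 9 | 45 + 1 = 46 | 45 | 45 / 45 |
| 10 | 55 + 1 = 56 | 55 | 55 / 55 |

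**2. Missing data do not break the tie.** A subject with missing visits contributes a submatrix of V, and V is unchanged. On simulated data (T = 5, n = 150, monotone missingness, illustrative V), the log-likelihood was −779.307973 for s²_b = 0, 0.2, 0.4, 0.6 and 0.8, with R positive definite each time. The smallest eigenvalue of the expected information matrix, evaluated without missing data, was about 1e-15 with the intercept and 0.036 without it.

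**3. Effect on the GMTs.** Setting s²_b = 0 already reaches every V that the larger model can reach. The maximized likelihood and the least squares GMTs are therefore the same with or without the intercept, provided the fit converges. In one simulated incomplete data set it did converge, from four starting values, with the same means and standard errors. Failure is a risk and not a certainty.

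**4. The named fallbacks with the intercept kept.**
- Compound symmetry: V = s²_e·I + (s²_c + s²_b)·J. Three parameters, rank 2: redundant again.
- First-order autoregressive: V_ij = s²·ρ^|i−j| + s²_b. Three parameters, rank 3 for T of 3 or more: identified.
- Both give one variance at every visit.

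**5. Why equal variance is doubtful (assumed inputs).** The documents give no SDs and no proportions below LLOQ. Take a normal log2 titer with latent SD 1.0 to 2.0, and set values below LLOQ to log2(LLOQ) − 1. The SD after substitution is:

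| Latent SD | 5% below LLOQ | 50% below | 75% below | Ratio 5% v 50% | Ratio 5% v 75% |
|---|---|---|---|---|---|
| 1.0 | 1.06 | 1.00 | 0.73 | 1.07 | 1.45 |
| 2.0 | 2.01 | 1.55 | 1.07 | 1.29 | 1.88 |

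The ratios are the same for LLOQ 1:8 and 1:16.

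**6. Illustration of an equal-variance fallback.** If a nominal 95% interval used the pooled variance, its coverage at a visit with standard deviation SD would be approximately

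2Φ(1.96·√(mean SD² over visits)/SD) − 1.

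Example: four visits, one high, ratio 1.88. Mean SD² = (3 + 1.88²)/4 = 1.634 and √1.634 = 1.278. Then 1.96 × 1.278/1.88 = 1.33, so coverage is 81.7%.

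| High-variance visits (of 4) | 1.07 | 1.29 | 1.45 | 1.88 |
|---|---|---|---|---|
| One | 93.8% | 89.9% | 87.3% | 81.7% |
| Two | 94.2% | 92.0% | 90.8% | 88.4% |
| Three | 94.6% | 93.7% | 93.2% | 92.4% |

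Low-variance visits cover 95.4% to 99.9%. These figures describe an equal-variance fallback however it is reached. They do not measure the effect of the random-intercept sentence.

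**The case against.** The case for leaving the text alone is that nothing changes if the fit converges, and the check fit did converge. The model is a secondary analysis in a descriptive study. The fallback list is open, so a careful analyst could drop the intercept or choose a better structure. The SAP introduction says programming rules are prepared separately, and these may settle the coding. All of this stands, and it keeps the point minor. It does not make the written model identifiable, and no text in either document removes the intercept when the matrix is unstructured. Nor can the unstructured matrix be read as the covariance of the random effects: the SAP ties it to the repeated measures, and a single intercept has only one variance.

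Three stronger readings are tempting but unsupported:
- A reader might infer that SAP 7.1 and 8.1.1 contradict the sentence. They do not. Both are silent on the covariance structure, and neither rules a random intercept in or out.
- A reader might infer that any Hessian warning sends the analysis to the fallback. The SAP's trigger is non-convergence; a warning on a converged fit triggers nothing.
- A reader might take the coverage figures as the damage done by this sentence. They rest on assumed SDs and would be the same if the unstructured model alone failed. SAP 8.2.3 also promises Type III output and least squares GMTs, and does not expressly plan model-based confidence intervals.

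**Conclusion.** The concern holds as a minor defect. The redundancy is algebraic: one surplus covariance parameter at every number of visits, with no assumption about the data. The consequence is conditional. It needs a convergence failure caused by the surplus term, whose probability is unknown, and then a fallback that fits worse than the unstructured matrix would have done. Under the assumptions above, an equal-variance fallback ranges from negligible to moderate error. The worst value, 81.7%, needs a latent SD of 2.0, one visit with 5% of titers below LLOQ and the other three with 75%.

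Only the sensitivity GMT model is touched. The primary proportions with Clopper-Pearson intervals and the per-visit GMTs with t-based intervals are unaffected.

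**What to change.** In SAP 8.2.3, delete the sentence that makes the intercept random and keep the unstructured covariance. Add a sentence that any fallback whose structure already contains the intercept variance, such as compound symmetry, is fitted without a random intercept. Preferably, also name a fallback with a separate variance at each visit, for example heterogeneous compound symmetry or heterogeneous first-order autoregressive. Robust standard errors are optional. They can be slightly small in small groups, and they do not remove bias in the means if the fallback correlation is wrong and data are missing at random.

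The deletion costs nothing: the same marginal covariances, and so the same maximum likelihood GMTs, remain attainable. The heterogeneous fallback costs a few more covariance parameters: at four visits, 4 variances + 1 correlation = 5, against 2 for either named structure and 10 for the unstructured matrix. No new data are needed and no primary result changes.
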